## **1. Statement of Purpose:**

This will be a randomized controlled trial examining the effect of an individually TTM-tailored intervention on the proportion of middle-age and older persons recruited from primary care practices and senior living communities who complete four ACP behaviors (completion of a living will, assignment of a health care proxy, and communication with loved ones and with their clinician about views on quality versus quantity of life) over six months, compared with usual care.

## **2. Background:**

Advance care planning (ACP), the process by which individuals and their healthcare surrogates can prepare for future treatment decisions, remains underutilized. ACP addresses many of the issues that patients and their caregivers endorse as important in end-of-life care, including clear communication with loved ones, achieving closure, and remaining in control of medical decisions. However, there are many emotional, cognitive, and practical barriers to engaging in ACP. While it has been demonstrated that intervention can increase ACP engagement, this model requires a skilled, well-trained moderator meeting with patients and caregivers in lengthy encounters. This type of intensive intervention may be best suited for patients with serious chronic illnesses who are ready to think about their specific disease trajectories and the decisions they are likely to face. The recent Institute of Medicine (IOM) report “Dying in America: Improving Quality and Honoring Individual Preferences near the End of Life” proposes a continuous process of ACP, starting earlier in the lifespan with individuals in good health and an initial focus on identification of a surrogate decision maker and general communication about patients’ goals with more in-depth and specific discussions coming later. This proposal describes the evaluation of an intervention to promote initial engagement in ACP. Taking a public health approach to ACP engagement, the intervention is designed to be able to reach a broad cross-section of individuals at modest expense.

The intervention builds upon the Principal Investigator (PI)’s long history of studying the process of ACP and several key insights provided by her past work. First, ACP has historically been conceptualized as the process by which patients could specify in advance the treatment they would want to receive if they became decisionally incapable. It consisted of completion of advance directives (AD), which are documents such as living wills and health care proxies. However, it has been shown that this completion of documents, while most likely necessary, is not sufficient to improve end-of-life outcomes. The PI has argued that, instead of having patients make premature treatment decisions, which cannot take into account the specific details of future health scenarios and the clinical judgment of healthcare practitioners, ACP should instead be focused on preparing patients and their surrogates to make the best possible “in-the-moment” healthcare decisions. This goal for ACP is best met by conceptualizing ACP as acts of communication, between patients and surrogates, and between patients and physicians, that focus not on preferences for specific treatments but rather on broader goals of care. Second, the intervention treats ACP as a health behavior utilizing the Transtheoretical Model (TTM) of health behavior change. The TTM provides a framework for the delivery of tailored intervention materials based on an assessment of an individual’s readiness to engage in ACP along with the attitudes and beliefs influencing the desire, motivation, and ability to engage. The potential for this approach was recognized in the IOM report. The PI and her co-investigators have developed a TTM-tailored expert system intervention with stage-targeted brochures and demonstrated the acceptability of these materials to a diverse cohort of older adults. The proposed study represents the

logical next steps in this work, by examining the efficacy of the intervention on increased engagement in ACP.

### 3. Research Plan:

#### **Participants and Recruitment**

Participants will be community-dwelling persons 55 years of age or older with an upcoming primary care visit in the NEMG practice or one of Yale New Haven Health System practices or individuals residing in senior living communities. Exclusion criteria include: a) severe hearing impairment, defined as being unable to participate in a telephone conversation; b) severe visual impairment, defined as being unable to read large-print materials; c) moderate to severe cognitive impairment, defined as either a diagnosis of dementia and/or short-term recall of <2/3 objects at 2 minutes d) primary language other than English, e) having completed all of the four ACP behaviors that are the focus of this study.

Participants will be recruited from eight pairs of primary care practices belonging to Northeast Medical Group, an accountable care organization that includes practices in New Haven and Fairfield counties, and Yale New Haven Health System, or located in senior living communities with each pair matched in terms of size, proportion of patients age 55 and older, and proportion of minority patients. Participants will also be recruited from similarly matched senior living communities. One site in each pair will serve as the intervention site, and the other as the control site.

Physicians will review lists of upcoming patients and asked to identify patients meeting eligibility criteria who do not meet exclusion criteria. Physicians and/or staff will give a flyer to eligible participants the day of their visit. For senior living communities, we will solicit volunteers following a presentation by the Principal Investigator performed in the facility providing general information about advance care planning.

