#### **Process of Consent/Accent**

For individuals recruited from practices, clinicians will provide their consent for potentially eligible persons to participate. If clinician consent is granted, then the clinician will be alerted when he/she is scheduled to see a potentially eligible and asked to obtain the patient's assent to talk to the research associate about the study following the appointment. If the patient has the time, the research associate will explain the study and complete a process of written informed consent and HIPAA authorization. If the patient would like to participate but does not want to stay and would prefer to be contacted later by telephone, we will consent the participant in person and call them at the pre-arranged time. If participant does not want to sign at that time the patient will be given copies of the written documents to review with the research associate by telephone to complete the process of consent, sending in the signed forms using a self-addressed stamped envelope.

Individuals in senior living facilities will meet with the research assistant at the facility at a time of their choosing to complete the process of written informed consent and HIPAA authorization. The informed consent process will consist of the research associate and potential participant reading through the consent form together, with the research associate highlighting the study procedures, potential risks, and participants' ability to withdraw. The associate will ask if the participant has any questions, and then ask several open-ended questions to assess the potential participant's understanding.

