
In addition to their tailored feedback report, participants will receive one of two brochures that provides stage-matched information for each of the three ACP behaviors. In comparison to the tailored feedback reports, the brochures contain information that is salient to participants in a given stage of behavior change regardless of their individual decisional balance or use of processes. The brochure for individuals who are not ready to engage in any ACP behavior is brief, focusing on descriptions of strategies to overcome attitudinal barriers to engagement in ACP and the positive consequences of engagement. The brochure also includes two stories, adapted from the PI's prior qualitative research. One illustrates the benefits to a spouse and children of her husband's engagement in ACP, and the second describes the regrets of a daughter whose mother did not engage in ACP. The second brochure, for individuals who are ready to engage in one or more ACP activities, provides strategies for participating in each activity. This brochure, for example, provides "words to use" to approach a health care proxy, and questions for individuals and their surrogates to discuss regarding goals of care. In addition, participants will receive a pamphlet developed for the individual to give to his/her (potential) surrogate. This pamphlet, written from the perspective of the individual, explains to the surrogate how he/she can help the individual engage in ACP. The time points for assessment were selected to provide

sufficient time for the participant to reflect and act on the feedback received while maintaining the momentum to move forward by not waiting too long to provide follow-up.

The baseline assessment and feedback will occur in person, directly after a scheduled office visit. The assessment will be done through a face-to-face interview with a trained research associate, who will enter participants' responses into a laptop computer. The expert system feedback report will be delivered immediately via a portable color printer. The follow-up assessments will be conducted by telephone, with delivery of the feedback report and brochures by mail.

The baseline assessment will also include questions assessing sociodemographic status, health status, and psychosocial status (see below).

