The six-month contact will assess participants for the outcome variables for the study, which is the stage of change for each of the four ACP behaviors. This contact will be performed by an interviewer who is blinded to the participant's group assignment.

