### **Outcome Measures**

The primary and secondary outcomes will be based on the participant's stage of behavior change for each of the four ACP behaviors targeted by the intervention materials (see **C.1.c.**) obtained at six months following the baseline assessment. The primary outcome will be the proportion of participants achieving the stage of action or maintenance for all four ACP behaviors. The secondary outcomes include the proportion of participants achieving each stage for each of the four ACP behaviors.

These outcomes will be obtained through participant self-report by an interviewer who is blinded to the participant's group assignment. Although there is a potential concern that social desirability bias could result in differential reporting by participants in the intervention and control groups, there are several reasons why self-report is the best way to ascertain outcomes. First, there is no gold-standard objective measure for these outcomes. There are no incentives for physicians to document communication with patients regarding values and goals, so that underreporting of this communication in the medical record is likely to be substantial. Physician and/or surrogate self-report of communication is subject to the same social desirability bias, especially for physicians in the practices randomized to the intervention. It would be possible to ask participants for copies of ADs, but, if the intervention is successful in increasing communication, these may be given to surrogates and not be immediately accessible. Second, the intervention minimizes the likelihood of social desirability bias. Because the feedback reports and brochures acknowledge the difficulties

associated with behavior change, they provide participants with the message of engaging in behaviors when they are ready to do so, rather than with a message of needing to accomplish a certain behavior. In addition to these outcomes, responses to the scales used for the assessment will be examined as secondary outcomes.

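### In the practices, clinicians who probably know their site's arm decide which patients are approached, so the arms may differ in readiness at entry, and the planned covariates only partly address this.

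*Combined protocol and SAP*

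**What the plan says.** **Allocation.** Sites are allocated within matched pairs (Participants and Recruitment): "One site in each pair will serve as the intervention site, and the other as the control site". Matching is on size, share of patients aged 55 and over, and minority share.

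**Entry in the practices.** Clinicians act at four points.
- Identification (Participants and Recruitment): "Physicians will review lists of upcoming patients and asked to identify patients meeting eligibility criteria who do not meet exclusion criteria".
- Invitation (same section): "Physicians and/or staff will give a flyer to eligible participants the day of their visit".
- Permission (Process of Consent/Accent): "clinicians will provide their consent for potentially eligible persons to participate". No criteria for granting or refusing it are given.
- Approach (same section): the clinician is asked to obtain the patient's "assent to talk to the research associate about the study following the appointment".

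**Timing.** Description of Intervention Group states: "The baseline assessment and feedback will occur in person, directly after a scheduled office visit". The site's arm must therefore be set before its patients are picked.

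**Blinding.** The only blinding described is at six months: "This contact will be performed by an interviewer who is blinded to" the participant's assignment. Outcome Measures repeats this. Nothing conceals the arm from clinicians, practice staff or the recruiting research associate.

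**Senior living communities.** Volunteers come forward after a talk by the Principal Investigator. No physician stands between them and the study.

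**Analysis.** Independent Variables lists sociodemographic, health and psychosocial covariates, plus family experience of end-of-life decisions. Analysis plans a baseline comparison of groups and a look at potential covariates. The number of ACP behaviors done at baseline appears only as a subgroup factor (Secondary Outcomes).

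**The concern.** Randomizing sites makes the patient populations of the two arms comparable on average. It does not make the enrolled patients comparable if someone who knows the arm influences who is enrolled. The trait at risk is readiness for ACP, on which the intervention is built and which should bear directly on the outcome. Clinicians may also know something about it, since one of the four behaviors is a conversation with the clinician.

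Everyone scores zero on the primary outcome at entry, because people who have completed all four behaviors are excluded. The baseline value of the outcome therefore cannot reveal or correct an imbalance in how close patients are to completing them. With an expected control rate of only 5%, a shift of one or two percentage points matters. A larger sample would not remove it.

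**Working it through.** **1. Do the clinicians know the arm?** The plan does not say so outright. Outcome Measures argues that physician self-report would suffer social desirability bias, "especially for physicians in the practices randomized to the intervention". That makes sense only if those physicians know their arm. The sentence is about reporting outcomes, so it does not prove awareness when patients are being listed. With allocation by site, no concealment text and feedback delivered at the baseline visit, awareness is a strong inference.

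**2. The plan's own sample size.** Inputs from Power and Sample Size: 5% v 15%, one-tailed alpha .05, power .80, 16 sites, 50 per site, 20% loss.
- Dropout step: 800 / 0.80 = 1000, as stated.
- Arcsine effect size: h = 2·asin(√.15) − 2·asin(√.05) = 0.344.
- Without clustering: n per arm = 2·((1.645 + 0.842)/0.344)² ≈ 104.3.
- The 400 per arm implies a design effect of 400/104.3 = 3.84. The ICC is not stated. Solving back gives (3.84 − 1)/49 = .058 with the normal distribution, or .050 with a t test on 14 df (16 sites − 2 arms). Power at ICC .05 with 14 df is 80.2%.

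The stated 800 is plausible but cannot be confirmed. An ICC of .05 is used below because it fits the plan's figure, and ICC 0 is shown as the other end of the range.

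**3. Illustration of selection with no treatment effect.** These inputs are assumptions, not figures from the documents: 25% of eligible patients are nearly finished and have a 15% chance of completing by Month 6. For the overall rate to be 5%, the others must complete at (.05 − .25×.15)/.75 = 1.67%. With a share s of nearly finished patients in the intervention arm:

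rate = s×.15 + (1 − s)×.0167

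The chance of a significant one-tailed result comes from the noncentral t on 14 df, with noncentrality h·√(400/(2·DE)). Here h is now the arcsine difference between this rate and 5%, and DE = 1 + 49×ICC, which is 3.45 at ICC .05 and 1 at ICC 0.

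| Share s, intervention arm | Rate, no effect | ICC .05 | ICC 0 |
|---|---|---|---|
| 15% | 3.7% | .017 | .006 |
| 20% | 4.3% | .030 | .019 |
| 25% (no selection) | 5.0% | .050 | .050 |
| 30% | 5.7% | .076 | .107 |
| 35% | 6.3% | .110 | .193 |
| 40% | 7.0% | .151 | .306 |

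**4. Scope.** The table applies the shift to the whole arm, but the physician route exists only in practices, and the practice share is not given. If half of each arm came from practices (assumed), shifts of 5, 10 and 15 points become 2.5, 5 and 7.5 points overall. The ICC .05 figures fall to about .06, .08 and .09.

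**5. Would the planned analysis correct it?** The listed covariates do not include baseline stage of change or number of behaviors done. Both can be derived from the baseline assessment, which uses the same stage-of-change scales in both arms (Description of Intervention Group, Description of Control Group).

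**The case against.** The strongest reply is that identifying patients is a screening task against listed criteria, not a free choice. That is fair for the list review. It does not cover the clinician's own consent, which has no criteria, or the step of obtaining assent.

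A second reply is that safeguards exist: matched pairs, a baseline comparison and covariates, including family experience that the plan describes as associated with readiness. The Primary Outcome section also allows for potentially important covariates. These help in part. Matching balances sites, not the patients picked within them. A baseline comparison can show a difference but cannot prevent one. No text commits the primary model to baseline ACP status.

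A third reply concerns direction. A reader might infer that selection must favor the intervention because its physicians would pick receptive patients. The documents do not support that. The Background presents the intervention as promoting initial engagement, so a physician could equally favor patients who have done least. The upper rows of the table show that this would make the test conservative. This objection stands.

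Finally, a reader might want the research associate kept unaware of the arm until after baseline. That does not fit the design. Once the associate prints a first report at a site, the arm is known for every later participant there. The masking questions on diet, activity and falls are described only for control assessments, so the associate needs the arm beforehand. This objection also stands.

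**Conclusion.** The plan as written leaves room for selection after allocation in the practices. Clinicians who probably know the arm control identification, permission and approach, and the covariate list omits the most direct baseline measures of readiness.

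Two stronger readings go too far. The documents do not state that clinicians know the arm, and they do not show that the whole trial is affected, because the senior living communities have no physician gate. (Volunteering there could also differ by arm, but by a separate route.)

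The direction and size of any bias are unknown. Under the assumed rates and the whole-arm shift, the false-positive rate is .08 to .15 at ICC .05 and .11 to .31 at ICC 0, against a nominal .05. It is lower if practices supply only part of each arm, and below .05 if selection runs the other way. The case for acting is that the safeguards are cheap and an imbalance is hard to repair after enrollment.

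**What to change.** 1. In the practices, limit clinician review and consent to striking out patients who meet a listed exclusion. Invite all others in order of appointment, with one flyer and one invitation script at all sites. Where feasible, do not announce the site's arm to clinicians and practice staff. Do not require the research associate to be unaware of it.
2. Keep a log by site and arm of patients listed, struck out (with reason), invited and consented, and report it.
3. Prespecify adjustment of the primary model for the baseline number of ACP behaviors done, or baseline stage of change. Both arms already supply these data.

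Cost: a little more logging and less clinician discretion over who is invited. Concealment from clinicians may weaken as patients share their reports, which is why the log and the adjustment are needed as well.

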#### **Process of Consent/Accent**

For individuals recruited from practices, clinicians will provide their consent for potentially eligible persons to participate. If clinician consent is granted, then the clinician will be alerted when he/she is scheduled to see a potentially eligible and asked to obtain the patient's assent to talk to the research associate about the study following the appointment. If the patient has the time, the research associate will explain the study and complete a process of written informed consent and HIPAA authorization. If the patient would like to participate but does not want to stay and would prefer to be contacted later by telephone, we will consent the participant in person and call them at the pre-arranged time. If participant does not want to sign at that time the patient will be given copies of the written documents to review with the research associate by telephone to complete the process of consent, sending in the signed forms using a self-addressed stamped envelope.

Individuals in senior living facilities will meet with the research assistant at the facility at a time of their choosing to complete the process of written informed consent and HIPAA authorization. The informed consent process will consist of the research associate and potential participant reading through the consent form together, with the research associate highlighting the study procedures, potential risks, and participants' ability to withdraw. The associate will ask if the participant has any questions, and then ask several open-ended questions to assess the potential participant's understanding.

### **Description of Intervention Group**

Participants enrolled at the intervention site will receive four contacts, at baseline, two, four and six months. Each of the first three contacts consists of an integrated assessment and intervention feedback report, using an expert system. This is a software system consisting of an assessment battery, normative data on which to base decision rules, and materials that can be assembled for feedback. The assessment battery includes the core TTM measures, including Stages of Change (how ready the participant is to engage), Decisional Balance (DB) (attitudes regarding the pros and cons of engagement), and Values/Beliefs (V/B) (medical and religious beliefs that can affect readiness to engage in ACP). Participants are assessed for four different behaviors that together represent complete ACP engagement: communication with loved ones about views on quality of life versus quantity of life, communication with clinicians about views on quality of life versus quantity of life, assignment of a health care surrogate, and completion of a living will. The system takes the results of the assessment and results in an individualized feedback report. For individuals in early stages of change for a given behavior, the feedback focuses on changing attitudes, a necessary prerequisite for changing behavior, by addressing common barriers and by reminding individuals they can engage in small steps. For individuals in later stages of change, the feedback provides specific actions they can perform. In addition, if the participant has engaged in one ACP behavior but not another, the feedback provides information on how they can utilize what they have already accomplished in order to help them participate in any remaining ACP activities. Participants with a low pros score receive feedback suggesting additional pros they may not have realized, while participants with a high cons score receive feedback providing general strategies for overcoming the most common barriers to ACP. Participants also receive specific feedback for up to three items they endorsed on the V/B scale. A general introduction provides a common opening for the feedback report, briefly describing ACP, why it is necessary, and why individuals should engage in ACP even when it seems too difficult to plan for declines in health and dying. Whereas the baseline feedback report provides individualized normative feedback, the follow-up reports also provide ipsative feedback, in which the participants' current responses are compared to prior responses and feedback is provided on progress over time.

In addition to their tailored feedback report, participants will receive one of two brochures that provides stage-matched information for each of the three ACP behaviors. In comparison to the tailored feedback reports, the brochures contain information that is salient to participants in a given stage of behavior change regardless of their individual decisional balance or use of processes. The brochure for individuals who are not ready to engage in any ACP behavior is brief, focusing on descriptions of strategies to overcome attitudinal barriers to engagement in ACP and the positive consequences of engagement. The brochure also includes two stories, adapted from the PI's prior qualitative research. One illustrates the benefits to a spouse and children of her husband's engagement in ACP, and the second describes the regrets of a daughter whose mother did not engage in ACP. The second brochure, for individuals who are ready to engage in one or more ACP activities, provides strategies for participating in each activity. This brochure, for example, provides "words to use" to approach a health care proxy, and questions for individuals and their surrogates to discuss regarding goals of care. In addition, participants will receive a pamphlet developed for the individual to give to his/her (potential) surrogate. This pamphlet, written from the perspective of the individual, explains to the surrogate how he/she can help the individual engage in ACP. The time points for assessment were selected to provide

sufficient time for the participant to reflect and act on the feedback received while maintaining the momentum to move forward by not waiting too long to provide follow-up.

The baseline assessment and feedback will occur in person, directly after a scheduled office visit. The assessment will be done through a face-to-face interview with a trained research associate, who will enter participants' responses into a laptop computer. The expert system feedback report will be delivered immediately via a portable color printer. The follow-up assessments will be conducted by telephone, with delivery of the feedback report and brochures by mail.

The baseline assessment will also include questions assessing sociodemographic status, health status, and psychosocial status (see below).

The six-month contact will assess participants for the outcome variables for the study, which is the stage of change for each of the four ACP behaviors. This contact will be performed by an interviewer who is blinded to the participant's group assignment.

